8.1. Discontinuation from Study Treatment

Discontinuation due to a hepatic event or liver test abnormality. Patients who are discontinued from using study drug due to a hepatic event or liver test abnormality should have additional hepatic safety data collected via EDC. Discontinuation of the study for abnormal liver tests **should be** considered by the investigator when a patient meets one of the following conditions after consultation with the sponsor designated medical monitor:

- ALT or AST >5X ULN
- ALT or AST >3X ULN along with one or more of the following criteria:
 - sustained for more than 2 weeks or
 - TBL >2X ULN or
 - prothrombin time >1.5X ULN or
 - the appearance of fatigue, nausea, vomiting, right upper-quadrant pain or tenderness, fever, rash, and/or eosinophilia (>5%)
- alkaline phosphatase (ALP) >3X ULN
- ALP >2.5X ULN and TBL >2X ULN
- ALP >2.5X ULN with the appearance of fatigue, nausea, vomiting, right quadrant pain or tenderness, fever, rash, and/or eosinophilia (>5%)

In addition, patients will be discontinued from the study drug in the following circumstances:

- White blood cell count $\geq 1.5X$ ULN or an increase in white blood cells above ULN and $>2X$ ULN from last predose measure
- Neutrophil or total lymphocyte count of $\geq 1.5X$ ULN or an increase in neutrophils or total lymphocytes above ULN and $>2X$ ULN from last predose measure
- Patient received concomitant medication listed in Exclusion Criteria
- Patient's failure to comply with protocol requirements or study-related procedures
- Termination of the study by the sponsor or regulatory authorities

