- ^c Serum pregnancy test at Screening and urine pregnancy test at subsequent visits.
- ^d If the result of the QuantiFERON®-TB Gold test is positive, the patient will be excluded from the study. If result is indeterminate, a single re-test will be allowed. If the result of the second test is positive or still indeterminate, the patient will be excluded from the study. Patients who have been vaccinated with BCG at any time in the past do NOT need to undergo testing. Documentation of previous vaccination is required.
- ^e On days when there is pre-dose PK sampling (at 1 week, 2 weeks, 4 weeks, 8 weeks and 12 weeks after the first dose), the dosing will be at the site after pre-dose sampling (patients will be instructed to not dose at home). The patients will be required to bring to the CRU their study treatment kit with all unused tablets. On all other days, patients should take their medication at approximately the same time in the morning. It is recommended (but not required) that the dose should be taken with food.
- ^f A full physical examination will be conducted at screening and on Week 4. Physical examination must include evaluation of the skin and mucus membranes. A physical examination may be performed at other visits at the investigator's discretion.
- ^g Height at screening visit only.
- ^h Single BP readings and other vital signs (in a seated position) on Day 1 and subsequent visits.
- ⁱ Single 12-lead ECG readings (in supine position, for at least 5 minutes prior to the ECG reading). The screening ECG may be repeated at the investigator's discretion. When scheduled at the same time, the following order of procedures is recommended: ECGs, vital signs, and blood collection (and/or other study procedures).
- ^j Clinical laboratory tests will include hematology, serum chemistry, and urinalysis.
- ^k Pre-dose samples are to be obtained at 1 week, 2 weeks, 4 weeks and 8 weeks weeks after the first dose of study drug. On the last day of dosing (Day 85/Week 12), the following samples are to be collected: pre-dose and 1, 2, 4, 8 hr post last dose. One sample will also be collected on weeks 2, 4, 6 and 8 weeks post last dose. One sample should be taken at the early termination visit, if applicable. Timing of PK sample collection may be adjusted based on clinical needs. Actual sampling dates and times must be accurately recorded.

3. Introduction

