7.2.1. Selection and Timing of Doses

Patients should take their medication at approximately the same time in the morning everyday. It is recommended (but not required) that the dose should be taken with food.

On days when there is pre-dose PK sampling (at 1 week, 2 weeks, 4 weeks, 8 weeks and 12 weeks after the first dose), the dose must be administered at the site after the pre-dose sample has been obtained. On all other days, patients must take their study drug at approximately the same time in the morning. It is recommended (but not required) that the dose should be taken with food. The study drug (tablet) should be swallowed whole, and should be taken with a glass of water.

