9.2. Adverse Events

A clinical trial AE is any untoward medical event associated with the use of a drug or drug delivery system in humans, whether or not it is considered related to that drug or drug delivery system.

The sponsor has standards for reporting AEs that are to be followed regardless of applicable regulatory requirements that may be less stringent.

Investigators are responsible for monitoring the safety of patients who have entered this study and for alerting sponsor or its designee to any event that seems unusual, even if this event may be considered an unanticipated benefit to the patient.

The investigator is responsible for the appropriate medical care of patients during the study.

Investigators must document their review of each laboratory safety report.

The investigator remains responsible for following, through an appropriate healthcare option, AEs that are serious or otherwise medically important, considered related to the study drug or the study, or that caused them to discontinue the study drug before completing the study. The patient should be followed until the event resolves, stabilizes with appropriate diagnostic evaluation, or is reasonably explained. The frequency of follow-up evaluations of the AE is left to the discretion of the investigator.

Lack of drug effect is not an AE in clinical studies, because the purpose of the clinical study is to establish treatment effect.

After the informed consent form (ICF) is signed, study site personnel will record via EDC the occurrence and nature of each patient's preexisting conditions, including clinically significant signs and symptoms of the disease under treatment in the study. In addition, site personnel will record any change in the condition(s) and any new conditions as AEs. Investigators should record their assessment of the potential relatedness of each AE to protocol procedure or study treatment via EDC.

The investigator will interpret and document whether or not an AE has a reasonable possibility of being related to study treatment, or a study procedure, taking into account the disease, concomitant treatment, or pathologies.

A "reasonable possibility" means that there is a cause and effect relationship between the study drug, study device, and/or study procedure and the AE.

The investigator answers yes/no when making this assessment.

Ratings of AEs will be based on the following 3-point severity scale:

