Although all AEs are recorded in the case report form or EDC after signing informed consent, SAE reporting to the Sponsor begins after the subject has signed informed consent and has received the study drug. However, if an SAE occurs after signing informed consent, but prior to receiving the study drug, AND is considered Reasonably Possibly Related to a study procedure then it MUST be reported.

Investigators are not obligated to actively seek AEs or SAEs in patients once they have discontinued and/or completed the study. Serious adverse events occurring after a patient has taken the last dose of study drug will be collected for 30 days after the last dose of the study drug. However, if the investigator learns of any SAE, including a death, at any time after a patient has been discharged from the study, and he/she considers the event reasonably possibly related to the study treatment or study participation, the investigator must promptly notify the sponsor and/or its designee.

Pregnancy (during maternal or paternal exposure to study treatment) does not meet the definition of an AE. However, to fulfill regulatory requirements any pregnancy should be reported following the SAE process to collect data on the outcome for both mother and fetus.

The designated medical monitor of the sponsor will monitor safety data throughout the course of the study. The sponsor and/or its designee will review SAEs within appropriate timeframes to meet reporting obligations imposed by regulatory authorities. All serious and unexpected AEs for this study will be reported to regulatory authorities in accordance with local laws, directives, and regulations.

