10.3.5.2. Pharmacodynamics

Pharmacodynamic analysis will be performed on the PD analysis set.

PASI and sPGA scores will be individually listed.

These parameters will be summarized, on observed values and on changes from baseline (pre-dose) values by treatment arms.

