6.3.1. Clinical laboratory assessments over time

Change from baseline for each of the hematology, clinical chemistry and the numeric urinalysis parameters will be derived for each of the post-dose time points using the pre-dose measurement as the baseline. Descriptive statistics for the measurement at baseline and the measurement and change from baseline at each post-dose time point will be tabulated.

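### The pre-dose-relative part of the mandatory white-cell stopping rules in Protocol 8.1 can never trigger a stop that the 1.5X ULN part has not already triggered

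*Protocol*

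**What the plan says.** Protocol 8.1 lists circumstances in which stopping study drug is mandatory. Two concern leukocytes, and each has two parts joined by 'or':

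- White cells: a count of at least 1.5X ULN, or "an increase in white blood cells above ULN and $>2X$ ULN from last predose measure".
- Neutrophils or total lymphocytes: a count of at least 1.5X ULN, or "an increase in neutrophils or total lymphocytes above ULN and $>2X$ ULN from last predose measure".

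Nothing else in the protocol or SAP restates or corrects these rules.

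The term 'predose' is used in two ways elsewhere. Protocol 10.3.5.2 summarises PASI and sPGA "on changes from baseline (pre-dose) values by treatment arms", and SAP 6.3.1 derives laboratory changes "using the pre-dose measurement as the baseline"; both equate pre-dose with baseline. Protocol 7.2.1 and footnote e of the Schedule of Activities use it for samples taken before that day's dose at Weeks 1, 2, 4, 8 and 12: "On days when there is pre-dose PK sampling", "the dose must be administered at the site after the pre-dose sample has been obtained".

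**The concern.** A rule that names the patient's earlier value, and separately requires the count to exceed ULN, looks designed to catch a large individual rise that is still below 1.5X ULN. As printed, the multiplier is attached to ULN. The threshold then sits above the first part of the rule, and both qualifiers are idle.

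At stake is a mandatory safety stop. A patient whose count rises several-fold into the range from 1.0X to 1.5X ULN need not stop. Sites that try to give the clause a meaning could also apply different rules: the literal text, twice the patient's value, or a rise of twice that value, each against either baseline or the previous visit. The drug acts on T and B cells (Protocol 3.2), and earlier dosing in psoriasis patients lasted 28 days (Protocol 3.3) against 12 weeks here, so a cell-count rule should operate as its authors meant.

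**Working it through.** **Inputs.** Both parts of each bullet come from Protocol 8.1. Laboratory tests on treatment are at Days 1, 8, 15, 29, 57 and 85 (Schedule of Activities). Planned response is 37.5% against 7.5%, with 27 patients per arm, 10% drop-out counted as non-response, and a one-sided Fisher's exact test at 10% (Protocol 10.1).

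**Notation.** U = ULN, c = current count, b = value before first dose, with b ≥ 0.

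**Step 1: the rule as written.** Part 1 is c ≥ 1.5U. Part 2 has two literal readings:

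- Rise of more than 2X ULN: c − b > 2U, so c > b + 2U ≥ 2U.
- Rise to more than 2X ULN: c > 2U.

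In both, c > 2U > 1.5U, so part 1 is already met. The condition c > U is implied as well. A grid check (b from 0 to 1.5U, c from 0 to 6U, steps of 0.01U) found no combination meeting part 2 without part 1 under either reading. The lowest count meeting part 2 was 2.01U.

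**Step 2: the multiplier placed on the patient's own value.** With multiple k, the combined stopping threshold is min(1.5U, max(U, k·b)). Part 2 adds stops only if k·b < 1.5U.

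| Intended meaning | k | Adds stops only if | Count above which a stop is required |
|---|---|---|---|
| Count above 2X baseline | 2 | b < 0.75U | 1.0U at b = 0.4U or 0.5U; 1.2U at 0.6U; 1.4U at 0.7U |
| Rise of more than 2X baseline | 3 | b < 0.5U | 1.0U at b = 0.3U; 1.2U at 0.4U; 1.35U at 0.45U |

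On the same grid, the highest baselines with added stops were 0.74U (k = 2) and 0.49U (k = 3), as the formula predicts.

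**Step 3: examples.**

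- From 0.4U to 1.3U: 1.3/0.4 = 3.25-fold. Stops under both meanings, not as written.
- From 0.5U to 1.3U: 1.3/0.5 = 2.6-fold. Stops with k = 2 only.

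**Step 4: the comparator.** Take 0.4U at baseline, 0.7U at the previous visit and 1.3U now. The ratio is 3.25 to baseline but 1.3/0.7 = 1.86 to the previous visit. With k = 2 the choice of comparator decides whether the patient stops.

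**Step 5: time to the next scheduled count.** The intervals are 7, 7, 14, 28 and 28 days. A count between 1.0U and 1.5U at Day 29 or Day 57 requires no stop, and the next scheduled test is nominally 28 days later.

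**Step 6: what extra stops could cost in power.** The diluted rates are 0.9 × 37.5% = 33.75% and 0.9 × 7.5% = 6.75%. Exact power per comparison at 27 per arm is 84.2%, in line with the plan's claim of at least 80%. If one active-arm patient is forced to non-response in addition to the 10% drop-out, power is 81.8%; with two it is 79.1%.

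**The case against.** The strongest reply is that no stated threshold is lost. The operative rule, stop at 1.5X ULN, is clear and stricter than the idle clause. The gap between 1.0X and 1.5X ULN exists only if the sponsor meant a multiple of the patient's own value, and the documents do not say so. Nor do they show that counts in that range are hazardous with this drug; Protocol 3.3 reports no clinically significant safety concern in earlier dosing. This stands to the extent that the redundancy is proven while the lost protection is conditional. It does not rescue the text, because if 1.5X ULN alone was meant, the clause should go.

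Second, there are backstops. "Investigators must document their review of each laboratory safety report" (Protocol 9.2), and "The designated medical monitor of the sponsor will monitor safety data throughout the course of the study" (Protocol 9.2.1). The investigator may withdraw a patient (8.2), safety is reviewed quarterly (9.4.5), and SAP 2.6 anticipates unscheduled laboratory visits. These reduce the risk, and the 28-day interval applies to scheduled tests only. None of them sets a leukocyte threshold.

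Third, baseline is the better reading of the comparator. Protocol 10.3.1 defines baseline as the last value before double-blind drug, SAP 6.3.1 uses pre-dose that way for laboratory data, and the contrary usage concerns PK samples. That is fair, and it makes the previous-visit reading the weaker one. It does not remove it, since 8.1 does not use the word baseline.

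Fourth, the power figures assume that a stopped patient has no determinable Week 12 response. Protocol 8 asks patients who stop treatment to complete follow-up, so non-response is not automatic. This also stands: the figures illustrate a possible cost of the fix and do not measure an effect of the present wording.

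**Conclusion.** The concern holds. In both bullets the second part lies wholly inside the first, so the rule operates as a single stop at 1.5X ULN. That conclusion follows from the printed words and needs no assumption beyond counts being non-negative.

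The practical size depends on intent, which is inferred. Rises into the range from 1.0X to 1.5X ULN would be missed for baselines below 0.75X ULN if a count above twice baseline was meant, and below 0.5X ULN if a rise of more than twice baseline was meant. The documents give no reference ranges or distribution of baseline counts, so the number of patients cannot be estimated. The defect is in a safety rule and leaves the planned type 1 error and the primary test untouched.

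**What to change.** In both bullets, attach the multiplier to the patient's own value and name the comparator, for example: *above ULN and more than 2X the last value before first dose (baseline)*. The sponsor's medical team should confirm whether a count above 2X baseline or a rise of more than 2X baseline (count above 3X) is meant. If neither is, delete the second part so that the rule reads as it operates.

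The change is to the wording of two bullets. No new tests are needed: all three cell counts are in Protocol Appendix 2 and are scheduled at every visit through Week 12. Deleting the clause changes no patient's management. Rewording it may add an unknown number of treatment stops, and under SAP 2.7 any such patient whose Week 12 response cannot be determined counts as a non-responder. The power figures in the working (81.8% with one such patient in an active arm, 79.1% with two) are what the medical team should weigh when choosing the multiple.

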8.1.1. Discontinuation of Inadvertently Enrolled Patients from Study Treatment

If the Sponsor or investigator identifies a patient who did not meet enrollment criteria and was inadvertently enrolled, a discussion must occur between the sponsor designate medical monitor and the investigator to determine if the patient may continue on investigational product. If both agree it is medically appropriate to continue, the investigator must obtain documented approval from the sponsor to allow the inadvertently enrolled patient to continue on investigational product.

8.2. Discontinuation from the Study

Patients may be withdrawn from the study if any of the following criteria are observed:

- Enrollment in any other clinical study involving an investigational product or enrollment in any other type of medical research judged not to be scientifically or medically compatible with this study.
- Participation in the study needs to be stopped for medical, safety, regulatory, or other reasons consistent with applicable laws, regulations, and good clinical practice (GCP)
- Investigator's decision: the investigator may decide that the patient should be discontinued from the study if, in the investigator's opinion, continuation in the study would be detrimental to the patient's well-being, in particular in case of an AE
- Subject decision: the patient requests to be discontinued from the study.
- Subject becomes pregnant while on study

Patients who are discontinued from the study may be replaced at the discretion of the Sponsor.

8.3. Patients Lost to Follow-up

Every effort must be made to contact patients who do not return for a planned visit and the reason for withdrawal should be documented in the EDC. The patient can only be declared as 'lost to follow-up' if the investigator has had no success in contacting the patient.

9. Study Assessments and Procedures

Section 2 lists the Schedule of Activities, with the study procedures and their timing (including tolerance limits for timing).

Appendix 2 lists the laboratory tests that will be performed for this study.

Unless otherwise stated in the subsections below, all samples collected for specified laboratory tests will be destroyed within 60 days of receipt of confirmed test results. Certain samples may be retained for a longer period, if necessary, to comply with applicable laws, regulations, or laboratory certification standards.

9.1. Efficacy Assessments

9.1.1. Primary Efficacy Assessment - Psoriasis Area and Severity Index (PASI)

Primary efficacy assessments will be based on the PASI.

The PASI is a proven and widely used tool to evaluate the severity of psoriasis (Hägg et al. 2017). The PASI scores the severity of disease on a scale from 0 to 72 (where a score of 72 indicates extreme disease severity) by combining assessments of extent of body-surface involvement in the head, trunk, arms, and legs together with the severity of desquamation, erythema, and plaque induration.

9.1.2. Exploratory Efficacy Assessments – Static Physicians Global Assessment (sPGA)

The static Physicians Global Assessment (sPGA) is a widely used scale in psoriasis clinical trials that defines the severity of disease from clear to severe.

9.2. Adverse Events

A clinical trial AE is any untoward medical event associated with the use of a drug or drug delivery system in humans, whether or not it is considered related to that drug or drug delivery system.

The sponsor has standards for reporting AEs that are to be followed regardless of applicable regulatory requirements that may be less stringent.

Investigators are responsible for monitoring the safety of patients who have entered this study and for alerting sponsor or its designee to any event that seems unusual, even if this event may be considered an unanticipated benefit to the patient.

The investigator is responsible for the appropriate medical care of patients during the study.

Investigators must document their review of each laboratory safety report.

The investigator remains responsible for following, through an appropriate healthcare option, AEs that are serious or otherwise medically important, considered related to the study drug or the study, or that caused them to discontinue the study drug before completing the study. The patient should be followed until the event resolves, stabilizes with appropriate diagnostic evaluation, or is reasonably explained. The frequency of follow-up evaluations of the AE is left to the discretion of the investigator.

Lack of drug effect is not an AE in clinical studies, because the purpose of the clinical study is to establish treatment effect.

After the informed consent form (ICF) is signed, study site personnel will record via EDC the occurrence and nature of each patient's preexisting conditions, including clinically significant signs and symptoms of the disease under treatment in the study. In addition, site personnel will record any change in the condition(s) and any new conditions as AEs. Investigators should record their assessment of the potential relatedness of each AE to protocol procedure or study treatment via EDC.

The investigator will interpret and document whether or not an AE has a reasonable possibility of being related to study treatment, or a study procedure, taking into account the disease, concomitant treatment, or pathologies.

A "reasonable possibility" means that there is a cause and effect relationship between the study drug, study device, and/or study procedure and the AE.

The investigator answers yes/no when making this assessment.

Ratings of AEs will be based on the following 3-point severity scale:

Mild	Awareness of sign or symptom, but it is easily tolerated; does not interfere with daily activities.
Moderate	Discomfort enough to slightly disrupt daily activities. Medical intervention and/or close follow-up may be considered.
Severe	Incapacitating with complete disruption of daily activities. Medical intervention and/or close follow-up likely.

Planned surgeries and nonsurgical interventions should not be reported as AEs unless the underlying medical condition has worsened during the course of the study.

If a patient's study drug is discontinued as a result of an AE, study site personnel must report this to sponsor or its designee via EDC, clarifying if possible, the circumstances leading to any dosage modifications, or discontinuations of treatment.

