9.2.1. Serious Adverse Events

Study site personnel must alert the sponsor or its designee of any SAE **within 24 hours** of investigator awareness of the event via a sponsor-approved method. Serious adverse event reporting to the sponsor begins after the patient has signed Informed Consent.

If alerts are issued via telephone, they are to be immediately followed with official notification on study-specific SAE forms. This 24-hour notification requirement refers to the initial SAE information and all follow-up SAE information. Patients with a serious hepatic AE should have additional data collected using the EDC (Section 9.4.5.1).

An SAE is any AE from this study that results in 1 of the following outcomes:

- death
- initial or prolonged inpatient hospitalization
- a life-threatening experience (that is, immediate risk of dying)
- persistent or significant disability/incapacity
- congenital anomaly/birth defect
- Important medical events that may not be immediately life threatening or result in death or hospitalization but may jeopardize the patient or may require intervention to prevent one of the other outcomes listed in the definition above. Examples of such medical events include allergic bronchospasm requiring intensive treatment in an emergency room or at home, blood dyscrasias or convulsions that do not result in inpatient hospitalization, or the development of drug dependency or drug abuse.

Previously planned (prior to the signing of ICF) surgeries should not be reported as SAEs unless the underlying medical condition has worsened during the course of the study.

The following terms will be utilized to assess the relationship of the SAE to administration of study treatment:

- **Probably related:** a direct cause and effect relationship between the study treatment and the AE is likely.
- **Possibly related:** a cause and effect relationship between the study treatment and the AE has not been demonstrated at this time and is not probably, but is also not impossible.
- **Unlikely:** likely to be due to another etiology.
- **Not related:** without question, the AE is definitely not associated with study drug.

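### Protocol 9.2 defines a reasonable possibility of relatedness as an existing causal link, which conflicts with the SAE scale in 9.2.1 and leaves unclear what counts as related

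*Protocol*

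**What the plan says.** Protocol 9.2 has the investigator judge "whether or not an AE has a reasonable possibility of being related to study treatment, or a study procedure". The answer is binary: "The investigator answers yes/no when making this assessment". The section defines the key phrase by saying that it "means that there is a cause and effect relationship between the study drug, study device, and/or study procedure and the AE".

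Protocol 9.2.1 gives a separate four-level scale for the relationship of an SAE to study treatment. In the top category, *probably related*, "a direct cause and effect relationship between the study treatment and the AE is likely". In the next, *possibly related*, the causal link "has not been demonstrated at this time and is not probably, but is also not impossible". The other two are *unlikely* and *not related*.

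Protocol 9.2.1 also makes two duties depend on relatedness. An SAE after consent but before study drug is covered if it occurs in that interval "AND is considered Reasonably Possibly Related to a study procedure then it MUST be reported". An SAE that the investigator learns of after the patient's discharge must be notified if "he/she considers the event reasonably possibly related to the study treatment or study participation". The trigger in both is a variant of the phrase in 9.2, and it is not itself defined.

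Protocol 9.2.1.1 identifies SUSARs as serious events that are not listed in the Investigator's Brochure and that the investigator identifies as related. It does not name the scale that decides this.

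SAP 6.2, under treatment-related TEAEs, counts an event as drug-related if the investigator rates it possibly, probably or definitely related.

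**The concern.** A term that speaks of possibility has been given a definition that speaks of fact. A single case can seldom show that a drug caused an event, so an investigator who applies the definition as written will answer no for most suspected reactions. For an SAE, that no can sit beside *possibly related* or *probably related* on the other scale, and nothing says which record prevails.

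Relatedness has consequences in this plan. It helps to decide which serious events are SUSARs, whether an SAE learned of after discharge must be notified, which AEs the investigator keeps following (one of several triggers in 9.2), and which events enter the SAP's drug-related table. Safety and tolerability are a secondary objective. Earlier dosing in psoriasis patients lasted 28 days (Protocol 3.3), against 12 weeks here, so suspected but unproven events are among the signals that the study should capture.

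**Working it through.** No arithmetic applies. The check sets the definitions side by side and asks how one event is classified under each.

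**Step 1: SAEs.**

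| Investigator's view of the SAE | Protocol 9.2, read literally | Protocol 9.2.1 scale | SAP 6.2 drug-related table |
|---|---|---|---|
| A causal link exists | yes | probably related (no higher category) | counted; *definitely* has no protocol counterpart |
| A causal link is likely | no | probably related | counted |
| Not demonstrated, not probable, not impossible | no | possibly related | counted |
| Another cause is likely | no | unlikely | not counted |
| Certainly not due to the drug | no | not related | not counted |

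The second and third rows conflict. The third row is the plainest case: 9.2.1 describes an event for which "a cause and effect relationship between the study treatment and the AE has not been demonstrated at this time", and 9.2 asks for exactly that missing relationship. The second row also fails, because a likely relationship is weaker than one that exists. So both of the categories that a reader would naturally take as related, two of the four, can be a no under 9.2.

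**Step 2: non-serious AEs.** The protocol gives them only the yes/no question, so there is no second protocol rating to contradict. The literal effect is that a suspected but unproven event is recorded as unrelated. The SAP's three grades cannot be derived from a yes/no answer, so its drug-related table cannot be built for these events from what the protocol describes.

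**Step 3: duties that depend on relatedness.** The two triggers in 9.2.1 use the undefined variant. Read through 9.2, they cover only events judged to be causal. Read through *possibly related* in 9.2.1, they cover any event for which causation is not impossible. Both readings are open. For SUSARs, 9.2.1.1 leaves the same choice unresolved.

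**Step 4: duties that do not depend on relatedness.** Protocol 9.2.1 requires notice of any SAE within 24 hours of awareness and collects SAEs for 30 days after the last dose, whatever their cause. AE monitoring runs to Day 141 (Schedule of Activities), which is 141 − 85 = 56 days after the last dosing day. The ambiguity therefore matters chiefly for SAEs learned of after discharge.

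For the pre-dose duty the position is less clear, because 9.2.1 contradicts itself on when SAE reporting starts: at consent in one place, and after consent and receipt of study drug in another. That is a separate inconsistency and also needs reconciling.

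**The case against.** The strongest reply is that investigators will not read the sentence literally. Section 9.2 itself speaks of potential relatedness and of a reasonable possibility, so the definition may be taken to describe the kind of link and not to demand proof. That is plausible in practice. But a definition exists to settle such doubt, and this one points the wrong way.

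A second reply is that the reach is limited. The secondary endpoint is TEAEs, defined without relatedness (Protocol 10.3.4; SAP 6.2), and no safety comparison is tested (SAP 6). This stands: the main TEAE summaries are unaffected.

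Third, the eCRF was not available for this review and may already collect a graded scale for all AEs. If so, the SAP table could be produced, but the conflict between 9.2 and 9.2.1 would remain.

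Three stronger readings are tempting, and the documents do not support them:

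- A reader might infer that the two conditional SAE duties are left with no content. They are at most narrowed, since events judged causal stay covered, and the step from the phrase in 9.2 to the variant in 9.2.1 is itself an inference.
- A reader might infer that every suspected event receives two opposite records. Only SAEs are rated on both protocol scales.
- A reader might infer that one yes/no answer merges drug and procedure. Section 9.2 mentions both but does not say that they share a field. The scale in 9.2.1 and the SAP rule each refer to study treatment alone, and the eCRF would be needed to settle it.

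**Conclusion.** The inconsistency is real and worth correcting. Protocol 9.2 states a rule which, applied as written, classes suspected but unproven events as unrelated and conflicts with two of the four categories in 9.2.1. No text ranks or maps the scales. The consequences are an unclear test of relatedness for SUSARs, an ambiguous trigger that is open to a narrower reading (chiefly for SAEs learned of after discharge), and a SAP rule that matches neither protocol scale.

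The size cannot be put as a number of events, because the documents give no event rates. The conclusion assumes a literal reading of the definition in 9.2 and, for the SAP table, that the data collected follow the protocol's description. It does not extend to the general 24-hour and 30-day SAE duties or to the main TEAE summaries.

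**What to change.** 1. In Protocol 9.2, reword the definition so that a reasonable possibility means that a causal relationship may exist and need not be demonstrated.
2. In Protocol 9.2.1, state that *possibly related* and *probably related* count as yes. It follows that *unlikely* and *not related* count as no.
3. Use that one defined term as the trigger for both conditional SAE duties in 9.2.1 and for relatedness in 9.2.1.1.
4. In SAP 6.2, align the drug-related TEAE rule with the scale actually collected: yes/no if that is what the eCRF holds for non-serious events. Drop *definitely* unless the category is added to the protocol.

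The cost is a few sentences across the two documents and a check against the eCRF. Slightly more events will be classed as related, which is the expected price of capturing suspicion and not only proof.
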